4.4.3.5 Barthel Index

The BI total score will be used to evaluate the proportion of patients with complete independence (defined as a score = 100) and will be summarized by treatment group. Observed percentages and adjusted risk difference will be presented. The adjustment will be performed in the same way as for the primary endpoint. Reasons for not performing the assessment of BI will be summarized.

4.4.3.6 Glasgow Outcome Scale

Raw GOS score will be summarized by treatment group, and include the percentage of patients having each GOS score, and the proportion of patients with good recovery. Observed percentages and adjusted risk difference will be presented. The adjustment will be performed in the same way as for the primary endpoint. Reasons for not performing the assessment of GOS will be summarized.

4.4.4 Subgroup Analyses

For the primary endpoint, consistency of treatment effect of alteplase will be evaluated by various pre-specified baseline covariates. The primary pre-specified variables and their analytic thresholds are defined by:

- Age group (< 65 vs. ≥ 65)
- Pre-treatment NIHSS score group (0-2 vs. 3-5)
- Last known well time to treatment group (0-2 hours vs. > 2 hours)
- Stroke subgroup (RISS vs. non-RISS)

Statistical Analysis Plan: Alteplase—Genentech USMA
19/ML29093 5/17/2017

Adjusted odds ratios by subgroup will be obtained from multivariable logistic regressions with the main effects for treatment, age, last known well time to treatment, and NIHSS, and fit separately for each level of the subgroup.

Interactions of IV alteplase treatment effect with each of the subgroup variables will be explored by adding interactions of the subgroup variables with treatment to the logistic regression. The interactions will be included one at a time; thus, there will be 4 separate models to test each interaction. Results from these models will not be reported, except when the interaction p-values is smaller than 0.1, in which case the p-values will be footnoted in the forest plot.

A forest plot will be constructed to visually illustrate the subgroup analyses. The plot will show the odds ratios described above with two-sided 95% CIs, corresponding to each level of these subgroups. The plot will also show the common odds ratio estimate in different color or line pattern, as a reference. A subgroup analysis will be conducted only if there is at least 10 subjects per outcome (mRS 0-1, mRS >1), and the standard error of the odds ratio estimate is stable with the addition of the covariates.

Analysis of the efficacy endpoints is summarized in [Table 2](#).

Table 2
Summary of Efficacy Analyses

Analysis	Statistical Method	Missing Data Method	Analysis Set(s)
Primary			
mRS 0-1 Day 90	Risk difference via linear regression, CI	LOCF + hot deck	ITT
Secondary			
mRS ordinal Day 90	Proportional odds model Descriptive, frequencies	LOCF + hot deck	ITT
Global outcome measure (Global test)	Logistic regression with a 4-dimensional outcome using GEE	LOCF + hot deck for mRS, non-response for death *	ITT
Exploratory			
mRS 0-1 Day 90	Logistic regression	LOCF + hot deck	ITT
	Logistic regression with Day 30 and Day 90 outcome using GEE	Repeated Measures Model (No imputation)	ITT
mRS 0 Day 90	Descriptive, the risk difference via linear regression OR via logistic regression	LOCF + hot deck	ITT
NIHSS 0, Day 90	Descriptive, the risk difference via linear regression OR via logistic regression	No imputation	ITT
NIHSS 0-1, Day 90	Descriptive, the risk difference via linear regression OR via logistic regression	No imputation	ITT
BI 100, Day 90	Descriptive, the risk difference via linear regression OR via logistic regression	No imputation	ITT

Statistical Analysis Plan: Alteplase—Genentech USMA
21/ML29093 5/17/2017

GOS 1, Day 90	Descriptive, the risk difference via linear regression OR via logistic regression	No imputation	ITT
---------------	---	---------------	-----

CIs = confidence intervals.

* A full analysis set approach will be used, so that patients with missingness of some but not all Day 90 endpoint components will be included in the model and contribute to the estimation of the common OR despite missing values on some of the end point components. Death before day 90 is considered as having not achieved the four binary end point components.

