2.3 DETERMINATION OF SAMPLE SIZE

The sample size was originally determined as follows.

A sample size of 856 is required in order to achieve 80% power in the primary analysis to detect effect size of 9% absolute difference in the proportion of patients with favorable outcomes [mRS of 0 or 1 at Day 90] between the alteplase and control arms. The above power consideration assumes a control proportion of 65% and Type I error of 0.025 (one-sided), and uses a group sequential design with one interim analysis for futility (non-binding), based on O'Brien and Fleming boundary, conducted after 50% of the anticipated sample size have completed 90-day follow-up assessments. [REDACTED] was used in sample size calculation.

The intention-to-treat principle will be applied to the primary analysis and, therefore, to safeguard against dilution of the treatment effect associated with an approximate 5% non adherence rate (due to loss to follow-up, consent withdrawal, treatment crossovers and stroke mimics), the above sample size was inflated by a factor of 1.108 (5). Therefore, a total sample size of 948 was planned for this study.

The study enrollment was terminated early in December 2016, after 313 patients were randomized. The analysis will be carried out based on all available data from patients randomized prior to termination. With this sample size, power calculations show that the study will be substantially underpowered to conduct superiority tests (Table 1). Therefore, all efficacy analyses will include estimation of treatment effects with the associated two-sided 95% confidence intervals.

Table 1			
Estimated Power for the Final Sample Size (N=313)			
Assumed Effect Size	7%	8%	9%
Statistical Power ^a	25%	31%	38%
^a Based on the t-test for the observed proportions of mRS 0-1 at Day 90, using type I error of 0.025, one-sided. Assumptions are based on a blinded evaluation of non-adherences in the Jan 2017 Development Safety Update Report (DSUR) dataset: - Control response rate among confirmed strokes is 74%. - 10% of randomized subjects are stroke mimics and 80% of those stroke mimics will have favorable outcome. - 1% of subjects received concomitant tPA - 7.4% subjects without Day 90 outcome (290 effective sample size)			

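### Subgroup odds ratios may be fitted with only 2.5 outcomes per predictor; Firth penalised likelihood would make these exploratory estimates more accurate at little cost

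*SAP*

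**What the plan says.** SAP section 4.4.4 examines the primary endpoint by age, baseline NIHSS, time to treatment and RISS status, two levels each. The odds ratios come from "multivariable logistic regressions with the main effects for treatment, age, last known well time to treatment, and NIHSS", and these models are "fit separately for each level of the subgroup". A forest plot shows each odds ratio with its 95% CI beside the common odds ratio.

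Two conditions in one sentence decide whether a level is analysed. The first is a count with both arms combined: "A subgroup analysis will be conducted only if there is at least 10 subjects per outcome (mRS 0-1, mRS >1". The second, which has no number attached, concerns precision once the model is adjusted: "and the standard error of the odds ratio estimate is stable with the addition of the covariates".

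The same section tests each treatment-by-subgroup interaction in its own model. Those results go unreported unless the p-value is below 0.1, when it is footnoted on the plot.

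The SAP names no estimation method beyond logistic regression, no penalised, exact or reduced model for sparse levels, and no expected subgroup sizes. The synopsis in Appendix A lists the subgroup analyses under exploratory objectives.

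**The concern.** Maximum likelihood, which is the default reading of logistic regression although the SAP does not name it, is biased away from an odds ratio of 1 in small samples. It is also erratic when there are few outcomes per predictor. The size rule was kept in a trial that stopped at about a third of its planned enrolment, so sparse levels are more likely than the design foresaw. The remaining guard cannot be applied reproducibly, because what counts as stable is left open and could be settled after the results are seen.

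At stake is how the forest plot reads. It places estimates from small levels next to a common odds ratio based on all patients, and many readers look first at the point estimates.

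**Working it through.** **1. Reproduce the plan's own figure.** The SAP gives no figure for the subgroup models, so the inputs were checked against Table 1 in section 2.3.
- Patients per arm: 290 / 2 = 145.
- Control rate: 0.9 × 0.74 + 0.1 × 0.80 = 0.746 (74% in confirmed strokes; "10% of randomized subjects are stroke mimics and 80% of those stroke mimics will have favorable outcome").
- Diluted effect: Δ = 0.9 × 0.99 × d = 0.891d (10% mimics, 1% concomitant tPA).
- Power = Φ((Δ − 1.96·SE0) / SE1), with SE0 pooled and SE1 unpooled.
- For d = 9%: Δ = 0.0802, SE0 = 0.0482, SE1 = 0.0479.

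| d | Computed | Table 1 |
|---|---|---|
| 7% | 24.6% | 25% |
| 8% | 31.1% | 31% |
| 9% | 38.4% | 38% |

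The inputs reproduce Table 1.

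**2. Outcomes per predictor at the floor.** 10 / 4 = 2.5.

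**3. How large a level is at the floor.** All 313 patients count, because missing mRS is imputed. Diluting for mimics only, the expected number with mRS >1 is:
- d = 9%: 313 × (1 − (0.746 + 0.081/2)) = 66.8
- d = 7%: 313 × (1 − (0.746 + 0.063/2)) = 69.6

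So 10 / 66.8 = 15.0% and 10 / 69.6 = 14.4%. A level holding about 15% of patients sits at the floor.

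**4. Bias at a fixed number of outcomes.** Simulation, 4,000 data sets per setting, about 22% with mRS >1. Assumed covariate log odds ratios per SD are −0.4, −0.3 and −0.2. The true odds ratio is 1.72, from (0.83/0.17) / (0.74/0.26), so the log odds ratio is 0.542.

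| Rarer outcome | Per predictor | Mean log OR, ML | Ratio to truth | Mean log OR, Firth | CI coverage, ML |
|---|---|---|---|---|---|
| 10 | 2.5 | 0.675 | 1.24 | 0.567 | 96.3% |
| 20 | 5 | 0.593 | 1.09 | 0.543 | 95.3% |
| 40 | 10 | 0.571 | 1.05 | 0.547 | 95.4% |

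At 10 outcomes the ML overstatement ranged from 20% to 32% over the covariate strengths and outcome prevalences tried at this odds ratio. At a true odds ratio of 1 and 10 outcomes, the mean log odds ratio was 0.005, so there is no average bias. Even so, 24% of ML estimates lay above 3 or below 1/3, against 16% with Firth.

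**5. Effect of the undefined stability condition.** It was read as a limit on the ratio of adjusted to unadjusted standard error. In a second run of the 10-outcome setting, the overstatement was 23% with no limit, 20% at 1.5, 14% at 1.25 and 13% at 1.1. With 35% of patients at mRS >1 and the 1.1 limit, it disappeared (ratio 0.96).

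**6. Whole-trial simulation.** N = 313, 23% with mRS >1, true odds ratio 1.65, no heterogeneity, 10-per-outcome rule applied, subgroup share assumed.
- *Bias in the log odds ratio, ML, before the stability check:* 16-25% at a 15% share and 13-20% at a 20% share across repeated runs. The mean is sensitive to a few extreme fits.
- *With a ratio limit of 1.25:* about 8-15% and 8-11%. *With 1.1:* close to zero (−3% and +6% in one run).
- *RMSE, ML against Firth, 15% share:* 0.891 and 0.727, a cut of 1 − 0.727/0.891 = 18%.
- *RMSE, 20% share:* 0.768 and 0.654, a cut of 15%.
- *RMSE, 15% share, after the check:* 0.787 and 0.664 at a limit of 1.25 (16%); 0.740 and 0.630 at 1.1 (15%).
- *True odds ratio 1, 15% share:* 0.831 and 0.698 (16%). Estimates wrong by more than three-fold fell from 18.2% to 11.8%.
- Over all settings run, the RMSE cut was about 12-18% at shares of 15-20%, 7-9% at 30% and 4-6% at 50%.

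**The case against.** Logistic regression with a minimum count and a standard-error check is ordinary practice, and nothing here contradicts the rest of the SAP. The bias is mostly a tail effect. In one run the median bias in the log odds ratio was 0.04-0.05 against median standard errors of 0.77 and 0.68. Coverage stays at 94-97%, so the plotted intervals are honest and very wide. A strict stability limit removes most of the mean bias. The analysis is exploratory and no decision rests on it. All of this stands.

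A reader might infer that the plan as written inflates small-subgroup effects by 20-25% and so creates apparent heterogeneity. The documents do not support that. No subgroup sizes are given, so no level is known to be near the floor, and naming RISS or the 0-2 hour level as small would be a guess. The 20-25% figure ignores the second condition in the same sentence. There is no mean bias when the true odds ratio is 1. The interaction models also give a check that does not come from the per-level fits, although it is shown only when p is below 0.1.

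What the objection leaves untouched is total error. Firth's RMSE was lower in every setting run, with or without the stability check. A strict limit also has a price: at 1.1 it discards about half of the otherwise eligible 15% subgroups.

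**Conclusion.** The point holds in a limited form. Section 4.4.4 allows fits at 2.5 outcomes per predictor, guarded by a condition without a criterion. For a level near the floor and a non-null effect, maximum likelihood overstates the log odds ratio by roughly 15-25% on average before the stability check, and by about 0-20% after it, depending on the cut-off. In the fixed-count runs the overstatement falls to about 9% at 20 outcomes and 5% at 40. Interval coverage is not harmed.

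The case for changing rests on accuracy, with an RMSE reduction of about 12-18% at 15-20% shares and 4-9% at 30-50% shares. These sizes rest on assumed subgroup shares, covariate effects, outcome prevalence and stability cut-offs, and on reading the SAP's logistic regression as maximum likelihood. This is a cheap improvement to an exploratory display and does not bear on the primary analysis.

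**What to change.** In section 4.4.4, state that the subgroup-level odds ratios in the forest plot are estimated by Firth penalised likelihood with profile penalised-likelihood 95% CIs. Keep the same covariates and the 10-per-outcome rule. The common reference odds ratio can remain the logistic estimate of section 4.4.3.1, or be shown by Firth with a footnote if the two differ. If the stability condition is kept, give it a numeric criterion before unblinding.

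The cost is one option in the logistic procedure and a sentence or two in the SAP. The downsides are slight shrinkage toward 1 and slightly conservative coverage (about 95-98% in simulation with Wald intervals).

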4.5 COGNITIVE, BEHAVIORAL AND PATIENT REPORTED OUTCOME ANALYSES

All the cognitive, behavioral and patient reported outcomes are considered exploratory.

4.5.1 Cognitive Assessments

A series of tests will be conducted at Day 90 to evaluate cognitive abilities of the patients. The tests and their outcomes are presented in the following table:

Table 3
Cognitive Assessments

Test	Outcome
Controlled Oral Word Association test	Number of words listed
Hopkins Verbal Learning test	Number of words recalled in 3 trials, Retention, and Recognition Discrimination Index
Digit symbol coding from the Wechsler Adult Intelligence Scale	Number of correctly coded digits
Forward and Backward Digit Span test	Maximum number of digits repeated, forward and backward scores
Benton Judgment of Line Orientation, form V	Total score
Animal Naming test	Number of unique animals named
15-item Boston Naming test	Total number of items answered correctly either spontaneously or after a stimulus cue

Outcomes from each test will be summarized by treatment group (mean, standard deviation, median, quartiles, minimum and maximum). Mean difference between treatment groups with 95% unadjusted normal CI will be presented. Reasons for the

Statistical Analysis Plan: Alteplase—Genentech USMA
22/ML29093 5/17/2017

assessment not being performed will be summarized by the number and percentage in each category.

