4.4.1 Primary Efficacy Endpoint

The primary efficacy analysis will estimate the effect of treatment with IV alteplase therapy and with the standard medical care (aspirin) in AIS patients with mild symptoms. The primary efficacy outcome is derived from the mRS.

The mRS is an assessment of disability with values from 0 (no symptoms at all) to 5 (severe disability); death will be scored as a '6'. The mRS is collected at 30 and 90 days after start of study drug administration. If death occurs prior to an assessment day (Day 30 or Day 90), the mRS will be considered available and will be set to 6.

The proportion of patients within each treatment group with a favorable outcome, defined by mRS of 0 or 1 at 90 days post-randomization, will be estimated in the IV alteplase arm and in the standard medical care arm. Reasons for not performing the assessment of mRS at Day 90 will be summarized.

The difference in proportions between the two groups will be estimated using the risk difference. The risk difference will be obtained from a linear model with the binary mRS 0-1 outcome as the response, treatment, and age, time from last known well to treatment, and baseline NIHSS as continuous covariates. Quadratic terms for the continuous covariates may be added to the model, if the Wald p-value for the quadratic term is <0.1. No interactions among the covariates will be included in this model.

A common approach for implementation of this model is binary regression, a GLM with the Bernoulli distribution for the outcome and the identity link function. This

Statistical Analysis Plan: Alteplase—Genentech USMA
14/ML29093 5/17/2017

model has a possibility of non-convergence when the estimated response probability falls outside of the (0,1) interval. To circumvent the non-convergence problem, an approach of using the ordinary least squares with a robust standard error is used in this study. It was shown that if a robust standard error is used with the ordinary least squares estimation, the estimate of the risk difference is equal or similar to the estimate from the GLM with an identity link for Bernoulli outcome approach (22, 23).

The primary efficacy analysis will include all ITT patients, with patients grouped according to the treatment assigned at randomization. Missing or out of window mRS at Day 90 will be imputed with LOCF or late Day 90 mRS, if available, or simulated with a hot deck method (see Section 4.7 for handling of missing mRS).

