4.4.2.1 Ordinal Modified Rankin Scale

As a secondary endpoint, mRS at Day 90 will be further explored on the range of the values (0 to 6) where the values of 5 and 6 are grouped. The distribution of full range of mRS scores at Day 90 (imputed) will be summarized by treatment group. Both tabular displays and stacked bar charts will be prepared.

Statistical Analysis Plan: Alteplase—Genentech USMA
15/ML29093 5/17/2017

The comparison will be achieved by fitting a proportional odds model with mRS score at Day 90 as the dependent variable, and treatment group, pre-treatment NIHSS score, age, and last known well time to treatment as the continuous predictors (1, 8). Quadratic terms for the continuous covariates may be added to the model, if the Wald p-value for the quadratic term is <0.1 . No interactions among the covariates will be included in this model. The adjusted odds ratio with its two-sided 95% CI will be shown. Direction of the odds ratio will be chosen to reflect change in the odds of achieving a lower (better) mRS if treated with IV alteplase.

The proportional odds assumption will be tested by the score test, and the p-value will be reported. If the proportional odds assumption does not hold, the resulting odds ratio will not be presented. The alternative analysis planned for this situation will provide the adjusted mean difference between mRS scores with two-sided 95% CI. Methodology for this estimation is similar to the primary outcome, but using the ordinal mRS as the dependent variable.

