Treatment comparisons will be performed considering the four binary outcome measures as 4 dimensions of the outcome endpoint (12). These dimensions will be assumed to have a common odds ratio adjusted for pre-treatment NIHSS score, age, and last known well time to treatment. Quadratic terms for the continuous covariates may be added to the model, if the Wald p-value for the quadratic term is < 0.1 . No interactions among the covariates will be included in this model. Estimation will be performed using generalized estimating equations for a logistic model with correlation between the four outcomes of the same patient. Details of this model can be found in Appendix D. The estimated common odds ratio and its two-sided 95% CI will be reported.

Each individual outcome measure will be evaluated separately: odds ratios with two-sided 95% CIs will be derived from a logistic model with the same covariates as used for the global outcome measure to facilitate interpretation of the results.

LOCF and hot deck imputation will be used for the missing mRS component, similarly to the primary analysis. No imputation is planned for the other missing components, other than the non-achievement imputation in the event of death. However, incomplete component sets can still contribute to the model and will be included.

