4.4.3.4 National Institutes of Health Stroke Scale

Descriptive statistics (n, mean, standard deviation, median, quartiles, minimum, and maximum) will be provided for NIHSS score by treatment group, both at Day 5 / Hospital discharge and at Day 90. Reasons for not performing the assessment of NIHSS at Day 90 will be summarized.

The NIHSS score will be used to evaluate the proportion of patients with a score = 0 vs 1 or higher, and separately, 0-1 vs. 2 or higher. Observed percentages and adjusted risk difference will be presented. The adjustment will be performed in the same way as for the primary endpoint. Adjusted odds ratio will be presented in a separate analysis for this outcome in the same fashion as for mRS 0-1.

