4.5.3.1 EQ-5D

Health-related quality of life will be assessed using the EQ-5D. The EQ-5D is a generic, preference-based health utility measure with questions about mobility, self-care, usual activities, pain/discomfort, and anxiety/depression that are used to build a composite of the patient's health status. The second component of the EQ-5D is a visual analogue scale (VAS), asking patients to rate their health from 0 to 100 where 0 represents the worst imaginable health state and 100 represents the best imaginable health state.

Each question is scored as 1 for no problem, 2 as some problem, and 3 indicating extreme problem. Ambiguous values (eg. 2 boxes are ticked for a single dimension) will be treated as missing (neither value used).

The 5 scores will then be converted into a single summary index by applying the time trade-off valuation technique for the US, published by EuroQol group. SAS

Statistical Analysis Plan: Alteplase—Genentech USMA
23/ML29093 5/17/2017

code to perform the calculation is provided in [Appendix G](#). The resulting summary index is a continuous variable ranging from -0.11 (i.e., 3 for all questions) to 1.0 (i.e., 1 for all questions) on a scale where 0.0 = death and 1.0 = perfect health (18). If any of the 5 scores are missing, the summary index will not be calculated and set to missing.

The VAS is scored by the crossing point of the VAS with the response line, or with a horizontal line extended from the end point of the response line. Ambiguous values (eg. the line crosses the VAS twice) will be treated as missing.

Scores to each question, the summary index, and the VAS result, will be summarized descriptively, and the two-sided 95% CI of the mean difference will be presented for the index and VAS.

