4.5.3.2 Stroke Impact Scale-16 (SIS-16)

Physical functioning will be evaluated using the SIS-16, which is a validated, stroke-specific, quality of life measure to assess the impact of stroke on a patient's health and life. Each of the 16 items is rated using the following scale: 1 = could not do at all; 2 = very difficult; 3 = somewhat difficult; 4 = a little difficult; 5 = not difficult at all.

The physical domain score is obtained by averaging the non-missing responses, provided that 9 or more questions are answered. The score is calculated as:

$$\text{Score} = 100 \times [(\text{Mean} - 1) / (5 - 1)]$$

which ranges from 0 to 100 (19).

Responses to individual questions and the physical domain score will be listed. The domain score will be summarized by treatment group and the two-sided 95% CI of the mean difference will be presented.

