4.5.3.3 Center for Epidemiologic Studies Depression Scale (CES-D)

The CES-D is a short, self-report scale designed to measure depressive symptomatology. Responses to the 20 individual items will be scored to obtain an overall depression assessment, as follows.

1. Assign scores 0 = rarely or none of the time, 1 = some or little of the time, 2 = occasionally or moderate amount of time, 3 = most or all of the time.

Statistical Analysis Plan: Alteplase—Genentech USMA
24/ML29093 5/17/2017

2. Reverse positive items by subtracting their score from 3. Positive items are 4, 8, 12, and 16.
3. If 4 or fewer items are missing, sum the available item scores to determine the total score. If more than 4 items are missing, no score is calculated.

The total score will be used to evaluate the proportion of patients with depressive symptoms (defined as a score of ≥ 16 at 90 days) and will be summarized by treatment group.

Observed percentages and adjusted odds ratio will be presented. The adjustment will be performed in the same way as for the exploratory analysis of mRS 0-1.

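### Cognition, walking speed, EQ-5D and SIS-16 get only a crude or unspecified mean difference, while the SAP's other efficacy models that name covariates adjust for age, NIHSS and time to treatment: an avoidable but minor loss of precision

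*SAP*

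**What the plan says.** Four sections of the SAP compare continuous Day 90 outcomes between arms.

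- **Cognitive tests (4.5.1) and 10-metre walk (4.5.2).** Both use the same sentence: "Mean difference between treatment groups with 95% unadjusted normal CI will be presented". The absence of covariates is explicit.
- **EQ-5D (4.5.3.1).** "the two-sided 95% CI of the mean difference will be presented for the index and VAS". No model or covariate is named.
- **SIS-16 (4.5.3.2).** "The domain score will be summarized by treatment group and the two-sided 95% CI of the mean difference will be presented". Again no model or covariate is named.

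Elsewhere the plan adjusts for the same three baseline variables:

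- The primary risk difference (4.4.1) comes from a linear model with "treatment, and age, time from last known well to treatment, and baseline NIHSS as continuous covariates".
- Ordinal mRS (4.4.2.1) uses "treatment group, pre-treatment NIHSS score, age, and last known well time to treatment as the continuous predictors".
- The global outcome (4.4.2.2) has a "common odds ratio adjusted for pre-treatment NIHSS score, age, and last known well time to treatment".
- NIHSS (4.4.3.4) follows the rule "The adjustment will be performed in the same way as for the primary endpoint", as do the Barthel Index and GOS (4.4.3.5, 4.4.3.6). The mRS 0 endpoint, the logistic model for mRS 0-1 and the subgroup models carry the three covariates too.
- CES-D (4.5.3.3) stands in the same part of the SAP as the four unadjusted sections and has the same exploratory status: "The adjustment will be performed in the same way as for the exploratory analysis of mRS 0-1".

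The SAP gives no reason for treating the continuous outcomes differently.

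**The concern.** Enrolment stopped at 313 of a planned 948 patients. Sections 2.3 and 4.4 accordingly turn the efficacy analyses into estimation with 95% confidence intervals, and interval width is then most of what an exploratory comparison offers. Age, baseline NIHSS and time to treatment are already collected, and the adjusted model is already written. If these variables explain some of the variation in cognitive scores, walking speed or quality of life, leaving them out makes the intervals wider than they need be.

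Exploratory status does not explain the choice, because CES-D has that status and is adjusted. For the primary endpoint the crude difference is supportive and stands beside the adjusted one. For cognition and walking speed it is the only estimate planned, and for EQ-5D and SIS-16 no adjusted estimate is named.

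**Working it through.** **The plan's own figures.** The SAP states no precision for these outcomes. The nearest figure is the effective sample size under Table 1: 313 × (1 - 0.074) = 289.8, stated as 290. With 145 per arm, one-sided alpha 0.025, 10% mimics with 80% favourable outcome in both arms, and 1% tPA crossover placed in the control arm, an assumed effect d gives a diluted difference of 0.9 × 0.99 × d. For d = 7%, 8% and 9% that is 0.0624, 0.0713 and 0.0802, with power 24.7%, 31.2% and 38.4%. Table 1 prints 25%, 31% and 38%, so 290 is a sound base. It refers to Day 90 mRS. Appendix B lets mRS be done by telephone but requires a visit for walking speed, so that count may be lower.

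**Unadjusted precision**, in units of the outcome SD, 1:1 allocation, N = 290:

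- SE = √(4/N) = √(4/290) = 0.117
- 95% half-width = 1.96 × 0.117 = 0.230

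**Adjusted precision.** Let R² be the share of outcome variance that the three covariates explain jointly. It is an assumption. Allowing for the cost of estimating three coefficients, the variance is multiplied by

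(1 - R²) × (1 + 3/(N - 6)) = (1 - R²) × (1 + 3/284) = (1 - R²) × 1.0106

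The width ratio is the square root of this factor, and the equivalent unadjusted N is 290 divided by it.

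| Assumed R² | Variance factor | Half-width (SD) | Change in width | Equivalent N |
|---|---|---|---|---|
| 0 | 1.011 | 0.231 | about +0.5% | 287 |
| 0.05 | 0.960 | 0.226 | about -2% | 302 |
| 0.10 | 0.910 | 0.220 | about -5% | 319 |
| 0.20 | 0.808 | 0.207 | about -10% | 359 |
| 0.30 | 0.707 | 0.194 | about -16% | 410 |

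**Break-even.** 1 - R² = 1/1.0106 gives R² ≈ 0.01. Above that, adjustment narrows the interval.

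**Simulation check.** With 3,000 trials per setting at N = 290, the mean width ratios were 1.005, 0.980, 0.953, 0.899 and 0.841. Coverage was about 95% for both the unadjusted and the adjusted interval throughout. The simulation used the ordinary least-squares standard error, so it confirms the precision arithmetic and does not test the robust option in Appendix G.

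**The case against.** The strongest reply is that nothing here is wrong. A difference in means from a randomised trial is valid, 4.5.1 and 4.5.2 specify it openly, and no decision rests on these outcomes. That stands, and it sets the severity.

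The reply can add that the plan follows a recognisable pattern: binary and ordinal outcomes are modelled, and continuous scores are given as simple differences. That is a fair description, but the SAP does not offer it as a reason. Section 4.4.2.1 also holds in reserve an adjusted mean difference for mRS by the primary method, so adjusting a non-binary score is not foreign to the plan.

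Four stronger readings are tempting, and the document does not support them:

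- **That chance imbalance in age makes these comparisons biased or the intervals too short.** The unadjusted standard error already allows for chance imbalance, and coverage in the simulation was about 95%. Section 4.3 also tabulates age, NIHSS and time to treatment by arm, so an imbalance would be visible.
- **That every other efficacy analysis is adjusted.** The crude risk difference is planned without covariates, and the repeated-measures model in Appendix D does not name its explanatory variables. The contrast holds for models that name their covariates.
- **That the SAP declares EQ-5D and SIS-16 unadjusted.** It does so only for cognition and walking speed. For the other two it follows from the absence of any model.
- **That the gain is known to be large.** The SAP gives no R² and no correlation of any of these scores with age. Eligibility also restricts two of the covariates (NIHSS at most 5, treatment within 3 hours), which may limit what they explain. One R² need not fit all these outcomes.

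**Conclusion.** The point holds as a minor, optional one. Cognition and walking speed are explicitly left unadjusted, and EQ-5D and SIS-16 have no covariates named. The inconsistency with CES-D and the main efficacy models is unexplained, and the plan probably gives away some precision. At about 290 patients the effect of adjusting runs from roughly 0.5% wider intervals if the covariates explain nothing to about 16% narrower at R² = 0.30. This range rests on assumed R² values, 1:1 allocation and a Day 90 count borrowed from mRS. The direction needs only a joint R² above about 0.01. The primary and secondary results are unaffected.

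**What to change.** In 4.5.1, 4.5.2, 4.5.3.1 and 4.5.3.2, state that the mean difference and its two-sided 95% interval come from the Appendix G least-squares model with robust standard error. Its terms would be treatment, age, baseline NIHSS and time from last known well to treatment. Fix linear terms in advance; carrying over the primary model's optional quadratic terms would add a data-driven choice for each of many scores. Keep the unadjusted difference beside it, as 4.4.1 does for the primary endpoint, and say explicitly that it is unadjusted for EQ-5D and SIS-16 as well.

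The cost is a few lines of SAP text, the existing code with a different response variable, and one extra column per table. The statistical downside is a negligible widening, about 0.5%, if the covariates explain almost nothing.
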